Hypothesis 3. Patients treated with valacyclovir will show less accumulation than patients on placebo in PET amyloid scans' (18F-Florbetapir, 0 to 78 weeks) combining six ROIs (SUVR: cerebellar reference) that show increased uptake in AD: medial orbital frontal, anterior cingulate, parietal, temporal, posterior cingulate, precuneus.

Hypothesis 4. From baseline to 78 weeks, patients treated with valacyclovir will show smaller increase in 18F-MK-6240 binding (SUVR: combining medial temporal, lateral temporal, prefrontal, parietal, and occipital regions of interest, ROIs, with cerebellar reference) than patients treated with placebo.

18F-MK-6240 PET imaging was funded by a grant supplement within the first year after study initiation and conducted in a subset of the overall sample.

In exploratory analyses, we will compare valacyclovir to placebo for changes in global cognition (MoCA), verbal memory (Craft story delayed verbatim recall), and examine age, sex and apolipoprotein E e4 genotype as a potential moderator of outcome. We will explore the AD "signature" of regional cortical thinning and whole brain cortical thinning on MRI for

valacyclovir compared to placebo. We will evaluate plasma acyclovir levels. In the subsample with CSF acyclovir levels, we will examine CSF acyclovir levels and if a sufficient number of participants has LPs done for CSF, plasma/CSF acyclovir correlations will be examined.

Inclusion Criteria:

- 1. Females must be postmenopausal defined as 12 consecutive months without menstruation.
- 2. Diagnosis of probable AD by NIA clinical diagnostic criteria.
- 3. Folstein Mini Mental State (MMSE) score 18 to 28 (inclusive) out of 30.
- 4. Clinical Dementia Rating (CDR) score of 1 (mild dementia).
- 5. A family member or other individual who is in contact with the patient and consents to serve as informant during the study.
- 6. Patient retains capacity to consent for him/herself or retains the capacity to identify a surrogate who will consent on his/her behalf.

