- 7. At screening, patients must test positive for serum antibodies to HSV1 or HSV2. Patients that test equivocal (index between 0.90-1.09; < 0.90 is negative and > 1.09 is positive) will repeat the test within 6 weeks at a repeat visit. If the results are negative at the second test, the patient will not enter the study. If the results are equivocal or positive at the second test (first test was equivocal), we will enroll the patient in the study because "equivocal" indicates the presence of antibodies that do not reach the minimum threshold.
- 8. Use of cholinesterase inhibitors and memantine, and concomitant psychotropic medications (other than high- dose benzodiazepines), will be permitted throughout the trial. Doses of these medications will need to be stable for at least 1 month prior to study entry. Any changes to the medication will be documented in the participant research chart. Medications given for other medical reasons, e.g., anti-diabetic or antihypertensive medications, will not be altered for the purposes of this trial and the patient's primary physician may adjust such medications as medically indicated throughout the trial. Details of concomitant medication use will be documented at all visits and will be available for statistical analysis.
- 9. For patients diagnosed with Mild Cognitive Impairment and CDR score of 0.5 (questionable dementia), if these patients have biomarkers of AD neuropathology with either a positive amyloid PET scan, positive fluorodeoxyglucose (FDG) PET scan of the brain, or positive findings for AD in CSF (low ABeta42 and high tau, p-tau protein levels) they will be eligible for the study. This applies to patients who already had an amyloid PET scan, FDG PET scan of the brain, or lumbar puncture, prior to recruitment into the protocol.

Exclusion Criteria:

- 1. Caregiver and/or participant is unwilling or unable to comply with study instructions.
- 2. Patient has dementia predominantly of non-Alzheimer's type, including vascular dementia, frontotemporal dementia, Lewy body dementia, substance-induced dementia.
- 3. Modified Hachinski scale score greater than 4
- 4. Current clinical diagnosis of schizophrenia, schizoaffective disorder, other psychosis, bipolar disorder or current major depression by DSM-5 criteria. Prior history of major depression will not be exclusionary (25% of older adults have a lifetime history of major depression).
- 5. Active suicidal intent or plan based on clinical assessment.

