Anti-viral Therapy in Alzheimer's Disease

NCT03282916

July 14, 2025

Statistical Analysis Plan for "Antiviral therapy: Valacyclovir Treatment of Alzheimer's Disease (VALAD) Clinical Trial"

1. Introduction.

The aim of the study was to evaluate the efficacy of Valacyclovir treatment in a 78-weeks, multicenter, randomized, double-blind, placebo-controlled, parallel-group treatment trial in participants with early Alzheimer's Disease (AD) and positive serum antibodies (IgG or IgM) to HSV1 or HSV2.

This statistical analysis plan provides more detailed descriptions of the statistical analyses conducted in the paper.

2. Study Design

One hundred and twenty participants with clinical diagnosis of probable AD or mild cognitive impairment (MCI), confirmed by a positive amyloid PET or FDG PET scan or a CSF AD profile, were randomized to Valacyclovir or placebo at 1:1 ratio. Block randomization with varying block sizes (2 and 4) was used to reduce the risk of treatment allocation prediction by clinicians. Participants were evaluated at five scheduled visits (weeks 0, 12, 26, 52, and 78). As a proof-of-concept study, the target dose of Valacyclovir was 4 g per day -- at the higher end of the usual oral dosing range. Treatment began at 2 g per day (1 g twice daily), with the dose increased by 1 g per day every two weeks until reaching either 4 g per day or the participant's maximum tolerated dose.

3. Outcome Measures.

1) Cognitive and functional measures:

- Alzheimer's Disease Assessment Scale Cognitive Subscale 11 (ADAS-Cog 11), assessed at weeks 0, 12, 26, 52, 78; scoring range 0-70, higher scores indicate greater cognitive impairment. (Primary)
- Alzheimer's Disease Cooperative Study-Activities of Daily Living Scale (ADCS-ADL), assessed at weeks 0, 12, 26, 52, 78; scoring range 0-78, higher scores indicate better daily functioning. (Secondary)
- Craft story delayed verbatim recall, assessed at weeks 0, 52, 78; scoring range 0-44, higher scores indicating better memory. (Secondary)
- Montreal Cognitive Assessment (MoCA), assessed at weeks 0, 52, 78; scoring range 0 to 30, higher scores indicating better global cognition. (Secondary)

For all cognitive and functional measures, the outcome of interest is the change from baseline at each follow-up time point. The primary endpoint is the change from baseline to 78 weeks.

2) Imaging measures:

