$$\Delta Y_{it} = \beta_0 + \beta_1 * Group_i + \alpha * Time_{it} + \gamma * Group_i * Time_{it} + \delta Y_{i0} + b_i + \epsilon_{it}, \tag{1}$$

where ΔY_{it} is change of the outcome measure (week t minus baseline) for subject i at timepoint t, $Group_i$ is the treatment group indicator for subject i (1= Valacyclovir and 0=placebo), $Time_{it}$ is the visit time point (treated as a categorical variable), Y_{i0} is baseline value of the outcome measure for subject i, b_i is a subject-specific random intercept, and ϵ_{it} is the unexplained

residual error term. $(\beta_0, \beta_1, \alpha, \gamma, \delta)$ are fixed effects parameters. The efficacy of Valacyclovir versus placebo at each time point was tested by forming contrasts of the fitted model. The model was further adjusted for key demographic and genetic variables, including age, sex, and apolipoprotein E $\varepsilon 4$ carrier status. Missing data on outcome variables were dealt with by using (longitudinal) linear mixed effects models which do not require complete measurements under the "missing at random" assumption.

For the primary outcome (ADAS-Cog 11), a series of sensitivity analyses were conducted to evaluate the robustness of the findings across key clinical subgroups and under different analytic assumptions. These included: 1) a per-protocol analysis limited to participants who completed the study; 2) a subgroup analysis of participants who received cholinesterase inhibitors or memantine; and 3) a subgroup analysis of participants with a baseline 18F-Florbetapir PET $SUVR \ge 1.15$ (amyloid positive for AD).

Linear regression analyses were performed to evaluate the effect of Valacyclovir on changes in imaging outcomes from baseline to 78 weeks. Each model included the baseline value of the corresponding imaging measure as a covariate to control for initial differences. The models were further adjusted for key demographic and genetic variables, including age, sex, and apolipoprotein E & carrier status. To assess the robustness of the findings and address potential bias due to missing data at follow-up, sensitivity analyses were conducted using weighted linear regression. In these models, the weights were calculated as the inverse probability of a subject being a completer, with probabilities estimated using logistic regression with ridge regularization to handle potential collinearity among baseline variables.

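### Biomarker evidence is required only on the MCI/CDR 0.5 route, yet the amyloid-positive subgroup is limited to ADAS-Cog11 and no model carries entry stage

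*SAP*

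**What the plan says.** **Entry.** The protocol's Inclusion Criteria give two routes. Items 2 and 4 admit participants on "Diagnosis of probable AD by NIA clinical diagnostic criteria" together with CDR 1; neither item asks for a biomarker. Item 9 admits MCI with CDR 0.5 given "either a positive amyloid PET scan, positive fluorodeoxyglucose (FDG) PET scan of the brain, or positive findings for AD in CSF", and adds: "This applies to patients who already had an amyloid PET scan, FDG PET scan of the brain, or lumbar puncture". The later section on Screening Eligibility again defines probable AD clinically.

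**Description of the sample.** SAP section 2, reproduced in the protocol's statistical section, has "probable AD or mild cognitive impairment (MCI), confirmed by a positive amyloid PET or FDG PET scan or a CSF AD profile".

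**Amyloid-positive analysis.** SAP section 5 plans "a subgroup analysis of participants with a baseline 18F-Florbetapir PET" SUVR of at least 1.15. It is one of three sensitivity analyses listed for the primary outcome, ADAS-Cog11.

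**Imaging.** Hypothesis 3 reads "Patients treated with valacyclovir will show less accumulation than patients on placebo in PET amyloid scans"; Hypothesis 4 makes the parallel statement for tau. SAP section 5 analyses each imaging change by linear regression adjusted for the baseline value of that same measure, then for age, sex and APOE ε4. An inverse-probability-weighted version addresses missing scans. There is no restriction by amyloid status.

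**Stage.** Model (1) has group, time, their interaction and the baseline outcome, with further adjustment for age, sex and APOE ε4. The exploratory moderators in the protocol are the same three variables. Randomisation is described as blocks of 2 and 4, with no stratification factor named. Table 1 schedules CDR at screening and florbetapir PET at week 0.

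**The concern.** The comma before the confirmation clause in SAP section 2 lets a reader take it as covering both diagnostic groups. Eligibility does not require that, so anyone quoting the sentence could describe the trial as one of biomarker-confirmed disease.

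The analysis gap matters more. Amyloid-negative participants can enter by either route, and the plan anticipates low values by defining a cut-off at all. Yet the restriction is applied to cognition and not to amyloid and tau PET, where amyloid status bears most directly on the hypothesis. If participants without amyloid pathology have little accumulation to slow, the full-sample PET effect understates the effect in those who have it, and no planned analysis would show this.

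The two routes are also two disease stages, which may well decline at different rates over 78 weeks. Stage is recorded at screening but enters no model, so some explainable variation is left in the residual.

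**Working it through.** **1. The plan's own figure.** SAP section 4 gives a detectable d of 0.50 at N = 130 and 0.52 at N = 120, for 80% power at 5%. Scaling gives 0.50 × √(130/120) = 0.520. A baseline-adjusted week-78 contrast (five visits, compound symmetry with r = 0.3, uniform dropout to 15%, two-sided 5% assumed) gives 0.506 at 65 per arm and 0.527 at 60 per arm. The figures are reproduced and are not in dispute. They concern ADAS-Cog11; the documents contain no PET effect size or power calculation.

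**2. Who needs a biomarker.**

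| Route | Biomarker required | Amyloid-negative entry possible |
|---|---|---|
| Probable AD, CDR 1 (items 2, 4) | none | yes |
| MCI, CDR 0.5 (item 9) | any one of amyloid PET, FDG-PET, CSF | yes, through FDG-PET |

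The protocol's section on obtaining amyloid reads also provides for cases where the positive/negative read and the SUVR interpretation disagree.

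**3. Dilution of a PET effect (illustration).** Assumptions, none of them from the documents: a share f is amyloid-negative with zero effect; the SD is common; d = 0.52 in amyloid-positive participants, borrowed from the cognitive outcome. The full-sample effect is 0.52 × (1 − f): 0.468 at f = 10%, 0.416 at 20%, 0.364 at 30%.

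Power ≈ Φ(d√(n/2) − 1.96), with n per arm. The full sample uses d(1 − f) and n; the subset uses d and n(1 − f).

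| f | 60 per arm: full / subset | 51 per arm (15% dropout): full / subset |
|---|---|---|
| 0 | 81% / 81% | 75% / 75% |
| 10% | 73% / 77% | 66% / 70% |
| 20% | 63% / 72% | 56% / 65% |
| 30% | 51% / 66% | 45% / 59% |

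The gain depends on the zero-effect assumption. If amyloid-negative participants have a fraction k of the effect, restriction helps only when √(1 − f) > 1 − f + fk. At f = 20% that is 0.894 > 0.80 + 0.20k, so k < 0.47. With about half the effect or more in the amyloid-negative group, restriction loses power.

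**4. Entry stage (illustration).** Assume an MCI share m of 15–45% and a difference in 78-week decline of 2–5 ADAS-Cog points. The SD of the chance between-arm difference in MCI share at 60 per arm is √(m(1 − m) × 2/60): 0.065 at m = 0.15, 0.084 at 0.30, 0.091 at 0.45. Multiplied by the difference in decline, the contribution to the treatment contrast has an SD from 0.065 × 2 = 0.13 to 0.091 × 5 = 0.45 points, before any baseline adjustment.

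For scale, assume a change-score SD of 6–10 points. The unadjusted standard error is then 6√(2/60) = 1.10 to 10√(2/60) = 1.83 points. Stage accounts for between 0.13²/1.83² ≈ 0.5% and 0.45²/1.10² ≈ 17% of that variance. Removing all of it would shorten the standard error by at most 1 − √(1 − 0.17) ≈ 9%, and by less once baseline ADAS-Cog11 is in the model, as planned.

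**The case against.** A reader might infer that the SAP contradicts the eligibility criteria. The documents do not establish that: the confirmation clause can attach to MCI alone, which agrees with item 9. The SUVR cut-off does not settle the reading either, since someone confirmed by FDG-PET could fall below it. The SAP's stated aim refers only to early AD with HSV antibodies and makes no biomarker claim. Ambiguity is the most that can be said.

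A reader might also infer that the plan has no amyloid-positive analysis. It has one, for the primary outcome.

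On imaging, the H3 model already contains baseline amyloid SUVR as a continuous covariate, and nothing in the documents says that people below 1.15 cannot accumulate amyloid. Both points stand, so it would be too strong to say that these participants cannot inform H3 or H4. But an additive covariate adjusts expected change; it does not let the treatment effect differ by amyloid status. The tau model contains baseline tau, not amyloid.

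On stage, chance imbalance under randomisation is already reflected in the standard error, and baseline ADAS-Cog11 is itself a severity measure. This also stands and limits the benefit to precision.

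Finally, the SAP is written in the past tense and makes no multiplicity adjustment. Restricted PET analyses would add at least three tests (amyloid, medial temporal tau, global tau) and may be post hoc. That is a reason to label them, not to omit them.

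**Conclusion.** The point holds as a matter of clarity and of two inexpensive gaps in the analysis. Biomarker evidence is required on one route only; the sample can include amyloid-negative people and spans CDR 0.5 and CDR 1; the planned SUVR subgroup stops at ADAS-Cog11; and no model uses entry stage.

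Its size is unknown, because the documents give neither the amyloid-negative nor the MCI share. The dilution to 0.47–0.36 and the power table rest on assumed shares of 10–30%, no effect in amyloid-negative participants, and a cognitive effect size applied to PET. Power for tau would be lower still, since tau PET was done in a subset. The stage figures rest on assumed shares and decline differences and overstate the gain, because they precede the planned baseline adjustment.

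A reader might take the missing stage term as a bias in the primary result. It is not: the ITT comparison remains valid under randomisation without it. What is affected is interpretation of the PET results, description of the population and, modestly, precision.

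**What to change.** 1. In SAP section 2 and its copy in the protocol, state that biomarker evidence was required only for the MCI/CDR 0.5 route. Report by arm the numbers per entry route and with baseline florbetapir SUVR of at least 1.15, and the number without a usable baseline scan.
2. Repeat the H3 and H4 regressions in participants with baseline SUVR of at least 1.15, as supplementary exploratory analyses beside the full-sample results.
3. Add screening CDR stage (0.5 or 1) as a covariate, with its interaction with Time, to model (1), and as a covariate to the imaging regressions.

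The cost is some wording and a few model runs on scheduled data (screening CDR and baseline florbetapir PET). The downsides are a few degrees of freedom; a smaller n in the restricted PET analyses, most of all for tau; and extra unadjusted tests, which must be labelled exploratory, and post hoc if added after unblinding.

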where ΔY_{it} is change of the outcome measure (week t minus baseline) for subject i at timepoint t, $Group_i$ is the treatment group indicator for subject i (1= Valacyclovir and 0=placebo), $Time_{it}$ is the visit time point (treated as a categorical variable), Y_{i0} is baseline value of the outcome measure for subject i, b_i is a subject-specific random intercept, and ϵ_{it} is the unexplained residual error term. $(\beta_0, \beta_1, \alpha, \gamma, \delta)$ are fixed effects parameters. The efficacy of Valacyclovir versus placebo at each time point was tested by forming contrasts of the fitted model. The model was further adjusted for key demographic and genetic variables, including age, sex, and apolipoprotein E $\epsilon 4$ carrier status. Missing data on outcome variables were dealt with by using (longitudinal) linear mixed effects models which do not require complete measurements under the "missing at random" assumption.

For the primary outcome (ADAS-Cog 11), a series of sensitivity analyses were conducted to evaluate the robustness of the findings across key clinical subgroups and under different analytic assumptions. These included: 1) a per-protocol analysis limited to participants who completed the study; 2) a subgroup analysis of participants who received cholinesterase inhibitors or memantine; and 3) a subgroup analysis of participants with a baseline 18F-Florbetapir PET $SUVR \ge 1.15$ (amyloid positive for AD).

Linear regression analyses were performed to evaluate the effect of Valacyclovir on changes in imaging outcomes from baseline to 78 weeks. Each model included the baseline value of the corresponding imaging measure as a covariate to control for initial differences. The models were

further adjusted for key demographic and genetic variables, including age, sex, and apolipoprotein E & carrier status. To assess the robustness of the findings and address potential bias due to missing data at follow-up, sensitivity analyses were conducted using weighted linear regression. In these models, the weights were calculated as the inverse probability of a subject being a completer, with probabilities estimated using logistic regression with ridge regularization to handle potential collinearity among baseline variables.

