The primary analyses will be on the ITT sample, i.e., all randomized subjects according to the treatment that they were assigned. Missing data on outcome variables will be dealt with by using (longitudinal) generalized linear mixed effects models that do not require complete measurements under the "missing at random" assumption. For MRI scan, 18F-Florbetapir PET scan, and 18F-MK-6240 tau PET scan, outcomes with just one pre and post measure, inverse probability weighting of cases with complete data will be used where weights are calculated based on the probability of a subject being a completer versus being a dropout. Sensitivity analysis will be performed to provide a range of plausible effect estimates that could arise due to non-ignorable missing data.

Treatment interruption for up to 6 weeks will be allowed for medical/surgical intervening conditions.

When a patient is at risk of dropping out:

When a patient is at risk of dropping out, study staff should assess the concern and take action accordingly, and the study doctor for that patient needs to be informed about intervening to keep the patient in the study if

possible. Staff should keep all relevant blank paper work for the week 78 or Endpoint (dropout) visit in the subject's chart at all times. While the goal is ITT assessments up to 78 weeks, in some cases this may not be possible, e.g., patient does not wish to return, patient moves to a distant location and clinic visits are no longer possible. In these instances, a final study visit should be completed whenever possible. This should be done even if not all procedures can be completed, e.g., patient is willing to come back for a final visit but does not wish to repeat the MRI or PET scan or LP. In this instance, complete all available forms and record them in the database after consultation with [name] as to which time-point the data should be entered in the database.

Assessment Instruments:

For a full reference of all forms, measures, requisitions, and notes kept for subjects participating in this protocol, please refer to the Mock Chart, which is kept in room 1600A at NYSPI. Testing materials for the ADAS-Cog11 and other procedures are stored in room 1600A.

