- ^{18F}Florbetapir PET SUVR: Mean standardized uptake value ratio (SUVR) from the medial orbitofrontal cortex, anterior cingulate, parietal lobe, posterior cingulate, temporal lobe, and precuneus, normalized to cerebellar gray matter.
- ^{18F}MK-6240 PET SUVR (Medial Temporal): SUVR averaged across medial temporal regions including the amygdala, hippocampus, entorhinal cortex, and parahippocampus.
- ^{18F}MK-6240 PET SUVR (Global Mean): SUVR global mean normalized to cerebellar gray matter.
- MRI Cortical Thickness: Mean cortical thickness across nine predefined brain regions.
- MRI Hippocampal Volume: Volume of the hippocampus.

All imaging measures were collected at baseline and 78 weeks. The outcomes are defined as the change in each measure from baseline to 78 weeks.

4. Sample Size Calculation.

The sample size calculation was based on the primary outcome: change in ADAS-Cog11 scores from baseline to 78 weeks, using the RMASS program for longitudinal studies. Assuming a within-subject correlation of r=0.3 (moderate correlation) for repeated measures and a uniform dropout rate reaching 15% by 78 weeks, a total sample size of 130 participants (65 per arm) was originally projected to detect Cohen's d of 0.50 with 80% power at 5% significance level. With approval from sponsor (NIA) and DSMB, the recruitment target was reduced to 120 participants due to pandemic-related recruitment delays and required study completion within the extended funding timeline. For n=120, the minimum detectable effect size increased slightly to a Cohen's d of 0.52.

5. Statistical analysis

The analyses were conducted on the Intent-to-treat (ITT) sample, i.e., all randomized participants according to the treatment that they were assigned. All hypotheses were tested at level of significance of 5%. There was no adjustment for multiple statistical comparisons in this trial. All analyses were conducted using R.

We first examined patients' baseline characteristics to ensure that covariates were balanced between treatment and placebo arms. Continuous variables were summarized using means and standard deviations, while categorical variables were summarized using counts and percentages.

Linear mixed effects models were used to evaluate the efficacy of Valacyclovir as compared to placebo on cognitive and functional outcomes. Specifically, for each outcome measure, we considered the following model

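### Model (1) leaves the residual covariance unstated; on its plain reading the week-78 test is mis-sized if the spread of change grows over 78 weeks, so state it and add an unstructured fit

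*SAP*

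**What the plan says.** SAP section 5 models change from baseline on group, categorical visit, their interaction and the baseline value. It adds a term b_i that "is a subject-specific random intercept" and a second random term that "is the unexplained residual error term". The same text stands in the protocol's Statistical Analysis Plan, section 5. Neither place gives a residual variance or correlation structure, a random slope, a robust standard error or a degrees-of-freedom method. The software is named only as R.

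The treatment tests come from this one fit: "The efficacy of Valacyclovir versus placebo at each time point was tested by forming contrasts of the fitted model". The primary endpoint is change to week 78 (SAP section 3), and the stated test level is "All hypotheses were tested at level of significance of 5" per cent.

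For ADAS-Cog11 the SAP says "a series of sensitivity analyses were conducted to evaluate the robustness of the findings across key clinical subgroups and under different analytic assumptions". The three it then lists are a completers analysis and two subgroup analyses. The protocol, under Intent to Treat/ Dropouts and Missing Data, adds: "Sensitivity analysis will be performed to provide a range of plausible effect estimates that could arise due to non-ignorable missing data". None of these varies the covariance, although the SAP list is worded as examples and need not be complete.

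**The concern.** A random intercept with independent, equal-variance residuals forces the same variance of change on every visit. In a progressive disease followed for 78 weeks, patients may well diverge, so that change varies more at week 78 than at week 12. A pooled variance is then too small for week 78 and too large for week 12. The primary p-value and confidence interval would look more precise than they are, and the early contrasts less precise. ADCS-ADL has the same four follow-up visits. MoCA and Craft story have only weeks 52 and 78, so the effect there is smaller.

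The SAP also relies on the mixed model for validity when data are missing at random. That protection assumes the covariance is right, so the estimate itself can be affected as well as its standard error.

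**Working it through.** **Inputs from the documents.** Two arms of 60; follow-up visits at weeks 12, 26, 52 and 78; 5% level (two-sided assumed). SAP section 4 plans with "Assuming a within-subject correlation of r=0.3 (moderate correlation) for repeated measures" and "a uniform dropout rate reaching 15% by 78 weeks".

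**Inputs assumed.** Total variance 45; slope SD s of 0, 2, 4, 6 or 8 points per 78 weeks; an alternative r = 0.8. No SD of change appears in the documents.

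**1. The plan's own figure.** With constant variance and r = 0.3, the baseline-adjusted variance is 1 - r² = 0.91 at every visit and the covariance is r - r² = 0.21. A week-78 contrast with d = 0.50, 80% power and uniform dropout to 15% needs 66.3 to 66.6 per arm, against the stated 65. For 120 participants, 0.50 × sqrt(130/120) = 0.52, as stated. This planning structure is compound symmetric, so model (1) fits it exactly and the test is correctly sized.

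**2. Error rate when variance grows (equal-variance reading).** Visit variance: v_t = 45(1 - r²) + s²(t/78)². The model uses the mean of v_t over the four visits. True error at visit t = 2(1 - Φ(1.96 × sqrt(mean v / v_t))).

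Worked case, r = 0.3 and s = 4:
- v = 41.33, 42.73, 48.06, 56.95; mean 47.27.
- SD ratio, week 78 to week 12: sqrt(56.95/41.33) = 1.17.
- Week 78: 1.96 × sqrt(47.27/56.95) = 1.79, giving 7.4%.
- Week 12: 1.96 × sqrt(47.27/41.33) = 2.10, giving 3.6%.

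By SD ratio (first figure: variance linear in time; second: quadratic, as with random slopes):

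| SD ratio | Week-78 error, % | Week-12 error, % |
|---|---|---|
| 1.00 | 5.0 | 5.0 |
| 1.05 | 5.6, 5.7 | 4.5, 4.6 |
| 1.17 | 7.0, 7.4 | 3.4, 3.6 |
| 1.40 | 9.3, 10.2 | 1.9, 2.2 |

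Reaching 10% at week 78 needs a ratio of 1.38 (quadratic) to 1.48 (linear).

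**3. Simulation.** True null, REML, non-informative dropout to 15%, 4,800 runs per scenario, t reference with visit completers minus 3 df. Age, sex and APOE adjustment was not simulated. Week-78 error at r = 0.3 for s = 0/2/4/6/8:
- Model (1), equal variance: 4.7/5.6/7.9/10.2/12.6%.
- Random intercept plus visit-specific residual variances: 4.8/5.1/6.0/6.9/7.5%.
- Unstructured: 4.7/5.2/5.5/5.2/5.2%.

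**4. What the scenarios are.** Only s = 0 keeps the planned r = 0.3. Adding slope variance raises the raw week 52-78 correlation to 0.34/0.43/0.53/0.63 for s = 2/4/6/8. For s = 4: (13.5 + 10.67)/sqrt(52.11 × 61) = 0.43. These are departures from the planning model.

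**5. Bias under missing at random.** A large-sample check let dropout depend on the last observed change in one arm only (assumed 21% against 15% dropout, no true effect). With the pooled-variance covariance, the week-78 difference was off by about 0.14-0.18 points at s = 4 and 0.37-0.61 at s = 8 (r from 0.3 to 0.8). When both arms dropped out alike, the bias was within noise. With non-informative dropout, the mean estimate stayed within 0.04 points of zero.

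**The case against.** A random intercept with categorical time is a recognised analysis, and it matches the constant-correlation structure used for planning. Harm needs two things that the documents do not state: that equal-variance residuals were fitted, and that the SD of change grows. Visit-specific variances may have been used. The high error rates come from assumed inputs: at r = 0.3 with s up to 4, the closed-form rate does not exceed 7.4%. All of this stands. It limits the size of the point, but the plan still does not let a reader tell which model was fitted.

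A reader might infer that the reported week-78 p-value is wrong, or that the true error is well above 10%. The documents do not support that: there is no visit-wise SD, and rates of that size need larger SD ratios that rest on more extreme assumptions. Nor can the inflated figures be attributed to the SAP's r = 0.3, which with constant variance gives 5.0%.

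The unstructured fit also has limits. Its level was checked with a simple t reference, not the Kenward-Roger or Satterthwaite df recommended below. In a separate simulation with 29% dropout, its week-78 error was 5.8-7.0%, so the df method should be named. In the flat-variance simulation its mean week-78 SE was 1.260 against 1.263 for the random intercept. A correctly specified smaller model cannot truly be less efficient, so this shows only that the cost is small.

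**Conclusion.** The omission is certain and sits on the primary test; its consequence is conditional. With a flat SD of change the 5% level holds. If the SD grows and one residual variance was fitted, week 78 is anti-conservative and week 12 conservative: at week 78 about 7.0-7.4% for an SD ratio of 1.17 and 9.3-10.2% for 1.4, both assumed ratios. Visit-specific residual variances would reduce this (6.0% against 7.9%, simulated, at r = 0.3 and s = 4). The week-78 estimate is not biased by this under non-informative dropout, but it can be under the SAP's missing-at-random assumption if dropout depends on earlier change differently by arm. It should be fixed because the remedy is cheap. Confidence is medium because the size cannot be determined from the documents.

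**What to change.** 1. State the residual covariance of model (1) as it was fitted.
2. Report the baseline-adjusted SD of change by visit and arm for ADAS-Cog11 and ADCS-ADL.
3. For both outcomes, report the week-78 contrast with an unstructured visit covariance (REML, Kenward-Roger or Satterthwaite df) beside model (1). The SAP is dated July 14, 2025 and written in the past tense, so label this analysis as added, and as post hoc if it was chosen after unblinding.
4. Do not choose between the two fits from the observed SDs. With 120 randomized and 15% dropout, the observed ratio has a 95% range of 0.83-1.20 when the true ratio is 1.00, and 0.98-1.41 when it is 1.17. The table can rule out a large problem but not a moderate one.
5. If the unstructured fit does not converge, use a less restrictive structure with visit-specific variances, such as heterogeneous Toeplitz or a random slope. A cluster-robust SE on model (1) repairs the interval only, not possible bias under missing at random.

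Cost: a few lines of R, one extra row and one SD table; ten covariance parameters instead of two; and two primary p-values on show. If variance grows, the week-78 interval widens, by about 10% at r = 0.3 and s = 4 (sqrt(56.95/47.27) = 1.10), and the week-12 interval narrows.
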